## 1. VERSION HISTORY

**Table 1. Summary of Changes**

Version/ Date	Associated Protocol Amendment	Rationale	Specific Changes
1.0 30 th Nov 2020	Amendment 2 (23 Sep 2020)	Original protocol was amended twice prior to first subject first visit	N/A
2.0 29 th Nov 2021	Amendment 2 (23 Sep 2020)	Updates based on SAP template update, Blinded Data Reviews and requirement for certain sites to derive QTcF manually and enter into CRF.	
Minor updates to page header and footers, section numbering and list of abbreviations.  Rationale: update to latest SAP template.
 
Sections 3.5.3.1 & 6.5.1: added parameters to list of endpoints.  Rationale: needed for reporting.
 
Section 3.5.5: included formula to derive QTcF for reporting.  Rationale: to ensure QTcF calculation is consistent across sites.
 
Sections 3.5.6, 6.6.5 & Appendix 6: included details on mental health assessment definitions and analyses.  Rationale: erroneously missed endpoints in version 1 of SAP.
 
Sections 3.5.3.2, 6.1.1.2.4, 6.1.1.2.5, 6.2.1.1, 6.3.1, 6.6.3 & 6.6.4: minor updates to definitions or inclusion of more details. Rationale: clarification.
 
Sections 6.1.1.2.4, 6.1.1.2.5.1, 6.1.1.2.8, 6.1.1.2.10, 6.5.4, 6.5.5, 6.6.2, 6.6.2.2, 6.6.3 & 6.6.4:

			
additional overall summarization included. Rationale: to provide an overview of the study population.
 
Section 6.6.2.1: added %change from baseline MMRM analyses for a subset of safety lab parameters. Rationale: permit a more comprehensive review of additional safety lab parameters.
 
Section 6.6.4: removed summaries of differences to placebo for ECG parameters. Rationale: MMRM analyses already included provide a more comprehensive assessment of these safety parameters.
 
Section 6.5.2: added summary table of important protocol deviations. Rationale: standard table required for CSR reporting.

--	--	--	--

## 2. INTRODUCTION

This statistical analysis plan (SAP) provides the detailed methodology for summary and statistical analyses of the data collected in Study C3421008. This document may modify the plans outlined in the protocol; however, any major modifications of the primary endpoint definition or its analysis will also be reflected in a protocol amendment.

### 2.1. Study Objectives, Endpoints, and Estimands

Objectives	Endpoints	Estimands
Primary:	Primary:	Primary:

 
To evaluate the tolerability of different titration schemes of PF-06882961 administered for 12 weeks to participants with T2DM and the tolerability of a single titration scheme in non-diabetic participants with obesity.
 
	
 
Incidence and severity of treatment emergent AEs.
 
	
 
There are no defined estimands for these endpoints and they will be analyzed using Pfizer data standards as applicable.
 

Secondary:	Secondary:	Secondary:

 
To evaluate the safety of different titration schemes of PF-06882961 administered for 12 weeks to participants with T2DM and the safety of a single titration scheme in non-diabetic participants with obesity.
 
	
 
Incidence of clinical laboratory abnormalities, vital signs (blood pressure and pulse rate) and ECG parameters (heart rate, QT, QTcF, PR and QRS intervals).
 
Assessment of mental health as determined by C-SSRS and PHQ-9.
 
	
 
There are no defined estimands for these endpoints and they will be analyzed using Pfizer data standards as applicable.
 

 
To evaluate the effect on fasting plasma glucose of different titration schemes of PF-06882961 administered for 12 weeks to participants with T2DM.
 
	
 
Change from baseline in fasting plasma glucose at Weeks 2, 4, 6, 8, 10 and 12.
 
	
 
Estimand 1A: This estimand is intended to provide a population level estimate of the mean treatment effect (PF-06882961 versus placebo) on a continuous endpoint in participants with T2DM on stable doses of metformin without the benefit of glycemic rescue medication while on treatment.
 


 
To evaluate the effect on HbA1c of different titration schemes of PF-06882961 administered for 12 weeks to participants with T2DM.
 
	
 
Change from baseline in HbA1c at Weeks 2, 4, 6, 8, 10 and 12.
 
	
 
Estimand 2A: This estimand will be the same as 1A.
 

 
To evaluate the effect on body weight of different titration schemes of PF-06882961 administered for 12 weeks to participants with T2DM.
 
	
 
Change from baseline in body weight at Weeks 2, 4, 6, 8, 10 and 12.
 
	
 
Estimand 3A: This estimand will be the same as 1A.
 

Objectives	Endpoints	Estimands

 
To evaluate the effect on body weight of a single titration scheme of PF-06882961 administered for 12 weeks to non-diabetic participants with obesity.
 
	
 
Change from baseline in body weight at Weeks 2, 4, 6, 8, 10 and 12.
 
	
 
Estimand 3B: This estimand will be the same as 1B.
 

Tertiary/Exploratory: 
 
To evaluate the effect on fasting plasma glucose of a single titration scheme of PF-06882961 administered for 12 weeks to non-diabetic participants with obesity.
 
	
 
Change from baseline in fasting plasma glucose at Weeks 2, 4, 6, 8, 10 and 12.
 
	Tertiary/Exploratory: 
 
Estimand 1B: This estimand is intended to provide a population level estimate of the mean treatment effect (PF-06882961 versus placebo) on a continuous endpoint in non-diabetic obese participants with obesity while on treatment.
 

 
To evaluate the effect on HbA1c of a single titration scheme of PF-06882961 administered for 12 weeks to non-diabetic participants with obesity.
 
	
 
Change from baseline in HbA1c at Weeks 2, 4, 6, 8, 10 and 12.
 
	
 
Estimand 2B: This estimand will be the same as 1B.
 


 
To summarize the pharmacokinetics of PF-06882961 in participants with T2DM and in non-diabetic participants with obesity.
 
	
 
Pre-dose plasma concentration of PF-06882961 on Days, 14, 28, 42, 56, 70, 84 and at 2-6 hours post-dose on Days 1, 42, 84.
 
	
 
There are no defined estimands for these endpoints and they will be analyzed using Pfizer data standards as applicable.
 

 
To enable exploratory research through collection of banked biospecimens, unless prohibited by local regulations or ethics committee decision.
 
	
 
Potential results from exploratory analysis of banked biospecimens (these results may or may not be generated in the context of the present study).
 
	

### 2.1.1. Primary Estimand(s)

N/A

### 2.1.2. Secondary Estimand(s)

*Estimand 1A will be the population average treatment effect on the change from baseline in fasting plasma glucose (FPG) of PF-06882961 compared to placebo in participants with T2DM in the absence of glycemic rescue medication while on treatment and stable doses of background metformin. This reflects a combination of the 'Hypothetical' and 'While on treatment' strategies as outlined in the ICH-E9 (R1) draft guidance.[1]*

*Measurements after initiation of glycemic rescue medication or discontinuation of IP will be censored and treated as missing data. Missing data due to censoring, study withdrawal or other reasons (eg, laboratory failure) will have data imputed based on a missing at random (MAR) assumption. Participants with inadequate compliance will have their fasting plasma glucose values used as-is in the analysis. The population-based treatment effect will be the difference in the mean change from baseline in each PF-06882961 arm compared to placebo. This estimand will be applied to the changes from baseline in FPG at Weeks 2, 4, 6, 8, 10 and 12.*

**Estimands related to other endpoints:**

*Estimands 2A and 3A will utilize the same approach as Estimand 1A for the associated endpoints. Similarly, Estimand 3B will utilize the same approach as Estimand 1B (described in Section 2.1.3) for the associated endpoint.*

The above estimands related to T2DM participants on a background of metformin (1A, 2A and 3A) include the following 4 attributes:

- Population: Defined by the inclusion and exclusion criteria to reflect participants with T2DM who are on a background of metformin
- Variable: Change from baseline at Weeks 2, 4, 6, 8, 10 and 12 for FPG, HbA1c and Body Weight for Estimands 1A, 2A and 3A, respectively
- Intercurrent events: Measurements after initiation of glycemic rescue medication and/or discontinuation of study investigational product (IP) will be censored
- Population-level summary: Difference of variable means between PF-06882961 (each treatment group considered separately) and placebo

**2.1.3. Additional Estimand(s)**

*Estimand 1B will be the population average treatment effect on the change from baseline in FPG of PF-06882961 compared to placebo in non-diabetic participants with obesity, while on treatment. This reflects a combination of the 'Hypothetical' and 'While on treatment' strategies as outlined in the ICH-E9 (R1) draft guidance.[1]*

*Measurements after discontinuation of IP will be censored and treated as missing data. Missing data due to censoring, study withdrawal or other reasons (eg, laboratory failure) will have data imputed based on a missing at random (MAR) assumption. Participants with inadequate compliance will have their fasting plasma glucose values used as-is in the analysis. The population-based treatment effect will be the difference in the mean change from baseline in each PF-06882961 arm compared to placebo. This estimand will be applied to the changes from baseline in FPG at Weeks 2, 4, 6, 8, 10 and 12.*

**Estimands related to other endpoints:**

Estimand 2B will utilize the same approach as Estimand 1B for the associated endpoints.

These above estimands related to non-diabetic participants with obesity (1B, 2B and 3B) include the following 4 attributes:

- Population: Defined by the inclusion and exclusion criteria to reflect non-diabetic participants with obesity
- Variable: Change from baseline at Weeks 2, 4, 6, 8, 10 and 12 for FPG, HbA1c and Body Weight for Estimands 1B, 2B and 3B, respectively
- Intercurrent events: Measurements after discontinuation of study IP will be censored
- Population-level summary: Difference of variable means between PF-06882961 (each treatment group considered separately) and placebo

## 2.2. Study Design

[figure not shown]
*This Phase 2a, multicenter, randomized, double-blind, sponsor-open, placebo-controlled, parallel-group, study will assess tolerability, safety, and pharmacodynamics (PD) of BID administration of PF-06882961 in adult participants with T2DM who are treated with metformin. In addition, participants with obesity, without T2DM, will be enrolled to explore differences in tolerability, safety, pharmacokinetics and pharmacodynamics between participants with T2DM and participants without T2DM and to support clinical development in both T2DM and obesity.*

*For participants with T2DM, the metformin dose (at least 500 mg/day) must have been stable for at least 60 days prior to the screening visit (Visit 1) and should remain the same until the first follow-up visit (ie, Visit 10, Week 13-14), except in circumstances where a dose change is deemed medically necessary.*

*Following the screening period to confirm eligibility (up to 4 weeks), the study will consist of a 2-week single-blind placebo run-in period, prior to randomization on Day 1. Following randomization, participants with T2DM will be assigned to either the placebo arm or 1 of the 5 active treatment arms with PF-06882961. PF-06882961 doses will be titrated to a target dose of 80 mg BID in 2 arms, 120 mg BID in 2 arms, and 200 mg BID in 1 arm.*

*Following randomization, participants with obesity will be assigned to either the placebo arm or an active treatment arm with PF-06882961 with a target dose of 200 mg BID.*

*The treatment period will be 12 weeks, followed by an approximate 4-week follow-up. The total duration of participation in this study is approximately 18 weeks, not including the screening period. Dosing with PF-06882961 or placebo will occur BID with food in the morning and evening. Refer to **Figure 1** for details of dose titration schemes per study arm, in which the doses depicted in Arms 1 to 7 are administered BID.*

**Figure 1. Dose Titration Scheme**

Assuming a 25% drop-out rate, approximately 140 participants will be randomly assigned to IP such that approximately 105 evaluable participants complete the study. Of these approximately 140 randomized participants, approximately 115 participants will have T2DM and approximately 25 will have obesity without T2DM. For participants with T2DM, approximately 20 participants will be allocated to each of the 5 active arms and approximately 15 participants to the placebo arm. For participants with obesity without T2DM, approximately 20 participants will be allocated to Arm 7 and approximately 5 participants to the placebo arm. To ensure balance between the groups, randomization will be stratified based on biological sex (men vs. women). There are no plans to replace withdrawn participants.

### 3. ENDPOINTS AND BASELINE VARIABLES: DEFINITIONS AND CONVENTIONS

*Baseline is defined as the result closest prior to dosing at Visit 3 (Day 1) for all endpoints, unless otherwise specified.*

#### 3.1. Primary Endpoint(s)

The primary endpoint is the incidence and severity of treatment emergent AEs per treatment group in participants with T2DM or non-diabetic participants with obesity. Adverse events are defined as per Section 3.5.1.

#### 3.2. Secondary Endpoint(s)

- Change from baseline in FPG at Weeks 2, 4, 6, 8, 10 and 12 in participants with T2DM.
- Change from baseline in HbA1c at Weeks 2, 4, 6, 8, 10 and 12 in participants with T2DM.

- Change from baseline in body weight at Weeks 2, 4, 6, 8, 10 and 12 in participants with T2DM.
- Change from baseline in body weight at Weeks 2, 4, 6, 8, 10 and 12 in non-diabetic participants with obesity.

For duplicate measurements of body weight, the average of the duplicate body weight readings collected at each assessment time will be calculated prior to summaries/analysis. If one of the two duplicates are missing, the non-missing value will be used, and missing values will not be imputed.

### **3.3. Other Endpoint(s)**

- Pre-dose plasma concentration of PF-06882961 on Days, 14, 28, 42, 56, 70, 84 and at 2-6 hours post-dose on Days 1, 42 and 84 in participants with T2DM or non-diabetic participants with obesity.
- Change from baseline in FPG at Weeks 2, 4, 6, 8, 10 and 12 in non-diabetic participants with obesity.
- Change from baseline in HbA1c at Weeks 2, 4, 6, 8, 10 and 12 in non-diabetic participants with obesity.

### **3.4. Baseline Variables**

Baseline measures will be included as a covariate in all applicable statistical models along with the stratification variable of female versus male (see Section 4.1).

### **3.5. Safety Endpoints**

#### **3.5.1. Adverse Events**

An adverse event is considered treatment emergent (TEAE) relative to a given treatment if:

- the event starts during the effective duration of treatment (i.e. starting after or on the first dose but before the last dose plus lag time)

The effective duration of treatment is determined by the lag time. Any event occurring within the lag time, whether this occurs during a break in treatment or at the end of treatment, is attributed to the corresponding treatment period. The lag time is defined by the Pfizer Standard of 365 days post last dose of IP.

Adverse events occurring during the placebo run-in period (i.e. from Day -14 up to the first dose of active treatment on Day 1) will be considered non-treatment emergent.

A 3-tier approach for summarizing AEs will not be used for this study as there is a low number of subjects planned to be enrolled per treatment group, although risk differences and related summaries for AEs of interest will be presented as defined in Section 6.1.1.2.2.

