### **10.3. Appendix 3: Adverse Events: Definitions and Procedures for Recording, Evaluating, Follow-up, and Reporting**

#### **10.3.1. Definition of AE**

AE Definition

• An AE is any untoward medical occurrence in a patient or clinical study participant, temporally associated with the use of study intervention, whether or not considered related to the study intervention.

• NOTE: An AE can therefore be any unfavorable and unintended sign (including an abnormal laboratory finding), symptom, or disease (new or exacerbated) temporally associated with the use of study intervention.

Events Meeting the AE Definition

• Any abnormal laboratory test results (hematology, clinical chemistry, or urinalysis) or other safety assessments (eg, ECG, radiological scans, vital sign measurements), including those that worsen from baseline, considered clinically significant in the medical and scientific judgment of the investigator (ie, not related to progression of underlying disease).

• Exacerbation of a chronic or intermittent preexisting condition including either an increase in frequency and/or intensity of the condition.

• New conditions detected or diagnosed after study intervention administration even though it may have been present before the start of the study.

• Signs, symptoms, or the clinical sequelae of a suspected drug-drug interaction.

• Signs, symptoms, or the clinical sequelae of a suspected overdose of either study intervention or a concomitant medication. Overdose per se will not be reported as an AE/SAE unless it is an intentional overdose taken with possible suicidal/self-harming intent. Such overdoses should be reported regardless of sequelae.

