#### **Follow-up of AEs and SAEs**

- The investigator is obligated to perform or arrange for the conduct of supplemental measurements and/or evaluations as medically indicated or as requested by the sponsor to elucidate the nature and/or causality of the AE or SAE as fully as possible. This may include additional laboratory tests or investigations, histopathological examinations, or consultation with other healthcare professionals.
- If a participant dies during participation in the study or during a recognized follow-up period, the investigator will provide Pfizer Safety with a copy of any postmortem findings including histopathology.
- New or updated information will be recorded in the originally completed CRF.
- The investigator will submit any updated SAE data to the sponsor within 24 hours of receipt of the information.

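### SAP 3.5.1 defines treatment emergence by start date alone, so whether a run-in AE that worsens on treatment enters the primary endpoint depends on how the site records it

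*SAP*

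**What the plan says.** SAP 3.1 builds the primary endpoint on TEAEs: "The primary endpoint is the incidence and severity of treatment emergent AEs per treatment group". SAP 3.5.1 gives the only criterion: "the event starts during the effective duration of treatment", explained as "starting after or on the first dose but before the last dose plus lag time". The far end of the window is wide: "The lag time is defined by the Pfizer Standard of 365 days post last dose of IP". For the near end, the SAP adds that "Adverse events occurring during the placebo run-in period" are non-treatment emergent, with no exception. SAP 3.5.1.2 (subset reporting interval) also works from start date only. Neither document has a clause for an event that is present before the first dose and becomes more severe afterwards.

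Two places in Protocol Appendix 3 bear on how such an event is recorded:

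- Section 10.3.1 lists as an AE: "Exacerbation of a chronic or intermittent preexisting condition including either an increase in frequency and/or intensity of the condition".
- Section 10.3.3, under follow-up of AEs and SAEs, says: "New or updated information will be recorded in the originally completed CRF".

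Protocol 8.3.1 and 8.3.1.2 start AE collection at informed consent and put all such events on the AE page. An event that begins in the run-in therefore has a record with a start date before Day 1.

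**The concern.** Every participant has a two-week placebo run-in with AE collection. Suppose a participant has mild nausea on run-in placebo that is still present at Day 1 and becomes severe during titration. Tolerability of titration is the primary objective, so this event should be seen. If the site updates the existing record, the start date stays before Day 1. The event then fails the start-date test and also falls under the run-in sentence. It contributes to neither the incidence nor the severity of TEAEs.

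The loss carries into the supplementary outputs, because SAP 6.1.1.2 restricts them to TEAEs of interest. These include first occurrence by week (6.1.1.2.4), weekly prevalence and severity (6.1.1.2.5) and the Week 1 table (6.1.1.2.5.1). The Week 1 table pools groups by 5 mg or 10 mg BID starting dose, a comparison the protocol sets out to make in 4.2 and 4.3. An event ongoing at Day 1 that worsens with the first doses belongs in that table.

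**Working it through.** **Plan figures used.** Protocol 9.2 gives about 20 participants in each of five T2DM active arms, 15 on T2DM placebo, 20 in Arm 7 and 5 on placebo in the obesity population: 5 × 20 + 15 + 20 + 5 = 140. With 25% drop-out, 140 × 0.75 = 105. Both match the plan. The plan states no figure on worsening, so the main check is a reading of the rules.

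**Same episode, two recordings.** Mild nausea starts on Day -5 and becomes severe on Day 3.

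| Recording | Start date tested | SAP 3.5.1 result |
|---|---|---|
| Original record updated (Protocol 10.3.3) | Day -5 | Not a TEAE |
| New exacerbation record (Protocol 10.3.1) | Day 3 | TEAE, severe |

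Nothing in either document chooses between the rows.

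**Weight of one participant** (100/n):

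- Arm of 20: 5.0 points.
- T2DM placebo, 15: 6.7 points.
- Obesity placebo, 5: 20 points.
- Week 1 table, pooled by starting dose from Protocol Table 2: T2DM 5 mg BID (Arms 1 and 3), 40 participants, 2.5 points; T2DM 10 mg BID (Arms 2, 4 and 6), 60 participants, 1.7 points; Arm 7 alone, 20 participants, 5.0 points.

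**How many participants might be affected.** The documents give no rate. Let q be the share of participants with a run-in AE that worsens on treatment (assumption). For an arm of 20, the expected number is 20q and the chance of at least one is 1 − (1 − q)^20.

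| q (assumed) | Expected in 20 | Chance of at least one |
|---|---|---|
| 1% | 0.2 | 18% |
| 5% | 1.0 | 64% |
| 10% | 2.0 | 88% |

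**Effect on any-TEAE incidence.** This changes only for a participant with no other TEAE. In Protocol Table 1 the active groups sum to 9+9+10+9+9+9+8+10 = 73 participants, of whom 6+8+10+8+8+9+8+9 = 66 had a TEAE (90%), leaving 7/73 = 9.6% without one. If having another TEAE is independent of having a worsened run-in AE (assumption), the loss is q × 0.096. That is 0.1, 0.5 and 1.0 points at q = 1%, 5% and 10%, or 0.02, 0.10 and 0.19 participants per arm of 20.

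**Effect on severity.** On the mild, moderate, severe scale in Protocol Appendix 3, an event that rises a category ends at moderate or severe. These categories are sparse. Protocol 2.2.2.1 reports 23 + 2 = 25 moderate or severe events out of 319 (8%) in 98 participants, or 25 × 20/98 = 5.1 events per 20 participants. That is a rough guide only, since C3421002 was shorter, used other doses and schedules, and the count includes placebo. Against about five such events per arm, one omitted event is visible.

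**The case against.** The strongest case on the other side has four parts.

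1. **Exacerbation is already an AE.** On the Protocol 10.3.1 wording, worsening after the first dose is its own event with an on-treatment start, and the existing rule counts it. This stands in part. It fits symptoms of a long-standing condition, such as GI complaints on stable metformin. It fits less clearly an acute symptom that began in the run-in, and nothing tells sites to open a second record.
2. **The follow-up sentence is general.** The Protocol 10.3.3 instruction sits among items on postmortem findings and updated SAE data, and it does not mention severity or start dates. This stands: the sentence favours keeping the original record but does not compel it. A reader might infer that every worsened run-in event is excluded. The documents do not support that; they leave the outcome open.
3. **Unseen sources may settle it.** The sponsor reporting standards and CRF instructions are not in the documents and may contain a worsening rule. That is possible, but the SAP's explicit definition does not have one.
4. **The events stay visible elsewhere.** SAP section 6 lists data collected before baseline, and 6.5.6 summarises AE-related discontinuations without a stated TEAE restriction. The rule is the same in all arms and the run-in precedes randomisation. All true, but neither output restores the event to the primary tables. An identical rule still removes more from active arms if the drug worsens symptoms more than placebo does.

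A reader might also assume that 5–15% have a run-in GI event and 30–50% of those worsen, and conclude that incidence is understated by 1.5–7.5 points (0.05 × 0.30 to 0.15 × 0.50). Neither rate is in the documents. The product counts participants affected, not incidence lost, because it ignores those who have another qualifying event.

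**Conclusion.** The point holds as a defect in a stated rule. As written, a run-in AE kept as one record that worsens on treatment is left out of the primary endpoint, while the same episode entered as a new record is included. The result therefore depends on site recording practice.

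The size is unknown. For any-TEAE incidence it is probably small: at most about 1 point for q up to 10%, given independence and the C3421002 rate of other TEAEs. The larger effect is on severity and on single-term nausea, vomiting and diarrhoea results. There, other TEAEs of a different term do not offset the loss, though a separate on-treatment episode of the same term would.

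If active drug worsens symptoms more than placebo does, the direction is to understate incidence and severity on the active arms. That is an expectation, not something the documents show. The change is worth making because it is cheap and concerns the primary endpoint.

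**What to change.** - **SAP 3.5.1:** add a second criterion, *or an event that started before the first dose and increases in severity on or after the first dose*. Make the run-in sentence subject to it, and mirror the clause in 3.5.1.2 within that section's own time window.
- **Onset and severity:** state that the onset of such an event is the date of worsening and its severity is that reached on treatment, so that it falls in the right week in 6.1.1.2.4 to 6.1.1.2.6.
- **Recording:** choose one convention, either a new record dated at worsening or a dated severity change on the original record. An undated overwrite would not show whether the increase came before or after the first dose.
- **Counting:** count each worsened episode once. If sites open a new record and the clause also makes the original treatment emergent, the AE-count tables in 6.1.1.1 would count it twice.
- **If data are already collected:** before unblinding the analysis, list AEs ongoing at Day 1 with their severity history, without treatment codes, to see whether any participant is affected.

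The cost is one SAP clause, one CRF-completion note and one blinded listing. The protocol does not itself define treatment emergence, but SAP section 2 requires major changes to the primary endpoint definition to appear in a protocol amendment. The sponsor should record whether it regards this as a clarification or a major change.
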